## LIST OF ABBREVIATIONS

E2	17-beta-estradiol
P4	progesterone
RCT	Randomized controlled trial
SITBI	Self-Injurious Thoughts and Behaviors Interview
UWRAP/LRAP	University of Washington Risk Assessment and Management Protocol/Linehan Risk Assessment and Management Protocol
EXP	Experimental
PL	Placebo
EMA	Ecological Momentary Assessment
CESD	Center for Epidemiologic Studies Depression Scale
BHI	Beck Hopelessness Inventory
STAI	State-Trait Anxiety Inventory
UPPS-P	An Impulsivity Scale measuring Urgency , lack of Premeditation , lack of Perseverance , Sensation seeking , and Positive Urgency .
SSES	State Self-Esteem Scale
FT-IRAP	Future-Thinking Implicit Relational Assessment Procedure (Hopelessness Task)
SAR-IAT	Social Acceptance and Rejection Implicit Association Test (Negative Social Appraisals Task)
SST	Stop-Signal Task (Inhibitory Control Task)
DPT	Dot Probe Task (Threat Sensitivity Task)
SCID	Structured Clinical Interview for Diagnosis
IDS	Investigational Drug Services

## STATEMENT OF COMPLIANCE

The trial will be conducted in accordance with the ICH E6, the Code of Federal Regulations on the Protection of Human Subjects (45 CFR Part 46), and the NIMH Terms of Award. The Principal Investigator will assure that no deviation from, or changes to the protocol will take place without prior agreement from the sponsor and documented approval from the Institutional Review Board (IRB), except where necessary to eliminate an immediate hazard(s) to the trial participants. All personnel involved in the conduct of this study have completed Human Subjects Protection Training.

## PROTOCOL SUMMARY

**Title:** Ovarian Hormone Withdrawal and Suicide Risk: An Experimental Approach

**Précis:** 45 female outpatients with suicidal ideation but minimal imminent risk for attempt will complete behavioral tasks measuring hopelessness, social appraisals, inhibitory control, and threat sensitivity as well as clinical interviews measuring suicidality in each of two conditions (order randomized across two menstrual cycle phases): (1) natural perimenstrual E2/P4 withdrawal (placebo), and (2) exogenous stabilization of physiologic premenstrual (luteal phase) E2/P4 to prevent withdrawal. Analyses will compare

	symptoms and suicidality under placebo to symptoms and suicidality under exogenous stabilization of E2 and P4.
Objectives:	The central aim of this mechanistic study is to experimentally test a pathophysiologic mediational model in which E2/P4 withdrawal increases perimenstrual suicidal desire (via increased hopelessness and negative social appraisals) and suicidal action capacity (via reduced inhibitory control and increased threat sensitivity). We predict that natural perimenstrual E2/P4 withdrawal (compared to stabilization) will be associated with greater perimenstrual suicidal desire (partially mediated by task performance indicating increased hopelessness and negative social appraisals) and action capacity (partially mediated by task performance indicating decreased inhibitory control and increased threat sensitivity).
Endpoint	Primary:
	
 
(1) Mean Within-Person Condition Difference (7 final placebo days – 7 final stabilization days) of SITB Suicidal Ideation subscale score (operationalization of suicidal desire)
 
(2) Mean Within-Person Condition Difference (7 final placebo days – 7 final stabilization days) of SITB Suicidal Planning subscale score (operationalization of suicidal action capacity)
 

	Secondary:
	
 
(1) Mean Within-Person Condition Difference (7 final placebo days – 7 final stabilization days) of BHI Hopelessness Score
 
(2) Mean Within-Person Condition Difference (7 final placebo days – 7 final stabilization days) of CES-D Depression Total Score
 
(3) Mean Within-Person Condition Difference (7 final placebo days – 7 final stabilization days) of UPPS-P Lack of Premeditation Impulsivity subscale
 
(4) Mean Within-Person Condition Difference (7 final placebo days – 7 final stabilization days) of PROMIS Anxiety Total Score
 
(5) Mean Within-Person Condition Difference (7 final placebo days – 7 final stabilization days) of SSEs Social Evaluation/ Rejection Sensitivity subscale
 

Population:	45 female outpatients with suicidal ideation but minimal  imminent risk for attempt
Phase:	N/A – Mechanistic Experiment

**Number of Sites enrolling participants:** 1

**Description of Study Agent :** Transdermal Estradiol .1mg/24hr weekly for two weeks, and Oral Micronized Progesterone 200mg (100mg each morning, 100mg each evening) for two weeks

**Study Duration:** 20 months

**Participant Duration:** ~3 menstrual cycles (1 menstrual cycle lasts, on average, ~28 days). Therefore, average participation will last roughly 3.5 months.

## SCHEMATIC OF STUDY DESIGN

### Screening and Enrollment

Perform initial telephone screen of potential subjects by inclusion and exclusion criteria, schedule enrollments as appropriate. At Enrollment, obtain informed consent if eligible and interested. Administer SCID, SITBI. Train participants in ovulation testing.

### Randomized Subject to a *Condition Order*

**Condition Order 1:** Placebo during visits 1-3, Experimental during visits 4-6 (n=15)

**Condition Order 2:** Experimental during visits 1-3, Placebo during visits 4-6 (n=15)

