**Design Overview:** 30 female outpatients with suicidal ideation but minimal imminent risk for attempt will complete behavioral tasks measuring *hopelessness, social appraisals, inhibitory control, and threat sensitivity* as well as clinical interviews in each of two conditions (order randomized across two menstrual cycle phases): (1) natural **perimenstrual E2/P4 withdrawal (placebo)**, and (2) **exogenous stabilization of physiologic premenstrual (luteal phase) E2/P4 to prevent withdrawal**. Daily calls will also assess symptoms and suicidality.

**CENTRAL HYPOTHESIS: Experimentally test a pathophysiologic mediational model** in which late luteal (perimenstrual) E2/P4 withdrawal (vs. experimental luteal E2/P4 stabilization) increases suicidal desire (via increased hopelessness and negative social appraisals) and suicidal action capacity (via reduced inhibitory control and increased threat sensitivity). We predict that natural E2/P4 withdrawal (compared to stabilization) will increase reports of suicidal desire (partially mediated by task performance indicating increased hopelessness and negative social appraisals) and action capacity (partially mediated by task performance indicating decreased inhibitory control and increased threat sensitivity).

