**4 STUDY DESIGN AND ENDPOINTS**

**4.1 DESCRIPTION OF THE STUDY DESIGN**

[figure not shown]
This is a single-center study; there is no phase designation because it is a mechanistic experiment with agents (E2,P4) that is commonly used in clinical practice.

**Participants:** 30 female outpatients with recent suicidal ideation but **low imminent risk for suicide attempt** (see **Human Subjects** section for details) receiving treatment as usual from a mental health provider at UNC will be recruited. Women must: be 18 to 45 years of age, have normal menstrual cycles (25-35 days), not pregnant (verified with urine screens), breastfeeding, or trying to get pregnant, not taking hormones, no history of serious medical illness, normal weight (BMI 18-28 kg/m^2), and low risk for thrombotic events (factor V Leiden mutation based on family history). Use of psychotropic medications are expected in the majority of participants. *Most outpatients with suicidality take psychotropic medications; therefore, to increase feasibility and generalizability, medication use will be carefully measured daily and covaried in analyses if common enough.*

**Psychiatric Diagnoses.** Women will undergo initial SCID-I and SCID-II interviews. *History of manic episode, psychosis (except dissociation), or substance abuse disorder will be exclusionary due to increased risk of suicidal crises.* Additionally, a self-report history of treatment for postpartum depression or a current diagnosis of premenstrual dysphoric disorder will be exclusionary, since these reproductive mood disorders could be characterized by a different pathophysiological pattern of sensitivity to ovarian steroid flux. On the basis of work by [name], we expect that 50 - 75% of our sample will meet criteria for major or persistent depressive disorder, ≥ 50% will meet criteria for BPD, and ≥ 25% will meet criteria for an anxiety disorder.

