### **INCLUSION OF WOMEN AND MINORITIES**

Men will not be included in this study, given the stated purpose of examining ovarian hormone withdrawal as a mechanism of suicidal risk in women. 45 women will be included in the study.

The UNC Center for Women’s Mood Disorders has a strong commitment to the enrollment of minority women in research projects, and this commitment will be reflected in this study. As shown below, the ethnic and racial composition of the population from which subjects will be recruited, including Orange, Durham, and Wake counties, is similar to the population of the United States as a whole.

Race/Ethnicity	Wake	Durham	Orange	Adjusted Average
White	70%	54%	78%	69%
Black or African American	21%	39%	12%	24%
American Indian/Alaska Native	1%	1%	1%	1%
Asian	6%	5%	7%	6%
Hispanic or Latino Origin	10%	14%	8%	11%

**The PI plans to recruit similar proportions of ethnic and racial minorities for the study. We have conservatively estimated our ability to recruit a sample that is 76% White, 20% Black or African American, 4% Asian, and with 8% identifying as Hispanic or Latina.**

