### 10.5 SAMPLE SIZE

An unlimited number of women will be screened. 45 women will be enrolled in the study, with the goal of 30 women completing the study.

Power analyses are described below; alpha is set at .05, power at 80%. The null hypothesis is no link between the study experimental condition and risk for suicidal ideation, intent, and planning; the alternate hypothesis is that hormone stabilization in the experimental condition will prevent flux in these suicide-related outcomes. Because no previous studies have examined the impact of experimental hormones on suicidality, we have conducted power analyses using existing effect sizes on related constructs (e.g., BPD features).

**Power Analysis.** For the contrast testing the primary hypothesis, we will have power to detect a conventionally medium-sized effect of hormone withdrawal ( $r = .30$ ;  $d = .60$ ) at 80% power with just 17 participants. The PI's previous work in women with BPD suggests that attrition could be as high as 25% across two conditions; should attrition be this high, enrollment of 22 participants would be required for adequate power. However, to improve generalizability of our findings and to ensure 80% power to detect small-to-medium effect sizes ( $r = .20$ ;  $d = .40$ ), we aim to include 30 completers (with 45 women randomized). This number is especially reasonable given the

much larger effects found in the candidate's recent studies for the effect of natural ovarian steroid changes (average  $r = .58$ ;  $d = 1.38$ ) on daily symptoms of depression, rejection sensitivity, anxiety, and impulsivity.

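### The schematic randomizes 15 women per order (30 in total) and Section 4.1 recruits 30, but the Protocol Summary, Section 5.3 and Section 10.5 give 45, with 30 as the completer target.

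*Combined protocol and SAP*

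**What the plan says.** Three places use 30.

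- The Schematic of Study Design, under the heading for randomization to a condition order, gives "Placebo during visits 1-3, Experimental during visits 4-6 (n=15" and "Experimental during visits 1-3, Placebo during visits 4-6 (n=15".
- Section 2.2, Design Overview, has "30 female outpatients with suicidal ideation but minimal", and describes these women as completing the tasks and interviews in both conditions.
- Section 4.1 has "30 female outpatients with recent suicidal ideation but", and says that they will be recruited.

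Three places use 45.

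- The Protocol Summary has "45 female outpatients with suicidal ideation but minimal" in the Précis and repeats 45 under Population.
- Section 5.3, in the part on inclusion of women and minorities, has "45 women will be included in the study".
- Section 10.5 enrols 45 with a goal of 30 finishing, and then says "we aim to include 30 completers (with 45 women randomized".

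Section 10.5 also contains a smaller calculation. It takes 17 participants as enough for d = .60, allows attrition of up to 25%, and concludes that "enrollment of 22 participants would be required for adequate power".

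Sections 4.1 and 10.6.1 give randomization to the investigational drug service and state no number per order. Section 10.1 says that there will be no separate SAP.

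**The concern.** The schematic and Section 10.5 both describe the number randomized, and they give 30 and 45. Neither is superseded text. The drug service needs a number per order to prepare the list and the blinded supplies, and the schematic is the only place that supplies one. With no separate SAP, no other planned document would settle the question.

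If the schematic were followed, the trial would randomize its completer target and lose women from there. Section 10.5 rests its power statement on 30 women finishing both conditions. Section 10.5 also does not explain how 45 relates to 30, because the only attrition rate it cites is 25%.

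**Working it through.** **Inputs.** From the schematic: 15 + 15 = 30. From Section 10.5: 45 randomized, 30 completers, attrition up to 25%, 17 participants for d = .60, and 22 after attrition. From Sections 10.4.1 and 10.4.2: a two-tailed test at .05 and a paired t-test.

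**1. The plan's own attrition figure.** The stated 22 comes out if 17 is multiplied up: 17 × 1.25 = 21.25, rounded up to 22. Dividing by the retained fraction gives 17 / 0.75 = 22.67, rounded up to 23. As a check, 22 × 0.75 = 16.5, just short of 17, and 23 × 0.75 = 17.25. The difference is one participant.

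**2. The link from 45 to 30.** The implied loss is 1 − 30/45 = 33.3%. At 25%, 45 randomized would leave 45 × 0.75 = 33.75 completers, and 30 completers would need 30 / 0.75 = 40 randomized. So 45 carries a margin beyond the cited rate.

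**3. The number per order under Section 10.5.** 45 / 2 = 22.5, so one order has 22 and the other 23. At the implied loss these leave 22 × 2/3 = 14.7 and 23 × 2/3 = 15.3, or about 15 completers each. The schematic's 15 per order is therefore what Section 10.5 would expect as completers.

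**4. Completers by number randomized.**

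| Randomized | 25% loss | 33.3% loss |
|---|---|---|
| 30 (schematic) | 22.5 | 20 |
| 45 (Section 10.5) | 33.75 | 30 |

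**5. Power, conditional.** Assume that d is the mean paired difference divided by the SD of the paired differences. The protocol does not say so. The two-sided paired t-test at .05 then gives:

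| Completers | d = .40 | d = .60 |
|---|---|---|
| 20 | .40 | .72 |
| 22 | .43 | .77 |
| 30 | .56 | .89 |

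If d is instead scaled to the raw SD, the paired effect is d / √(2(1 − ρ)), where ρ is the within-person correlation. The protocol gives no ρ. For 30 completers and d = .40, power runs from .56 at ρ = 0.5 to .92 at ρ = 0.8. The scaling moves the levels, but fewer completers lower power under any of them.

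**The case against.** The strongest reply is that the protocol is clear where it matters. Section 10.5 is the controlling section. It gives 45 twice and names 30 as the completer goal, and the Protocol Summary and Section 5.3 agree with it. On this view the 30s are completer counts printed without a label, and nobody would stop the list at 30.

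Much of this stands. It makes 45 the likely intent, and Section 2.2 can be read as describing completers. It does not clear the other two places. The schematic prints its numbers under a randomization heading, and Section 4.1 speaks of recruitment. The wording of Section 2.2 is also not a reliable sign of completers, since nearly the same sentence in the Précis carries 45.

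A reader might infer three stronger points that the documents do not support.

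- *That the attrition arithmetic in Section 10.5 fails.* The 22 follows from a common shortcut, is off by one, and is superseded by the next sentence, which sets the 30-completer plan.
- *That 45 contradicts the 25%.* Section 10.5 never derives 45 from 25%. The rate is applied only to the step from 17 to 22, and 45 is more generous than it requires. The margin is unexplained, but it errs on the safe side.
- *That the intent-to-treat set is itself defined as 30 in one section and 45 in another.* Section 10.3 gives no number, and the only prose that states a number randomized is in Section 10.5.

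**Conclusion.** The point holds as a minor inconsistency in a number that the trial relies on. The figure of 15 per order matches the completer target and is printed as the number randomized. If it were used for the randomization list, about 22 women would complete at 25% attrition, or 20 at a one-third loss, which is 8 to 10 short of the target of 30. That result assumes that attrition applies to all randomized women at one of those two rates.

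It would be tempting to conclude that the trial will be underpowered because of this. The documents do not support that. The shortfall arises only if the list is built to the schematic against three other sections, and the power values above depend on a scaling of d that the protocol leaves open. Under that scaling, 30 completers give .56 at d = .40, where Section 10.5 claims 80%. That is a separate question about the effect-size definition and is not settled here.

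**What to change.** - **Schematic:** replace n=15 in each order with *22–23 randomized (about 15 completers expected)*.
- **Sections 2.2 and 4.1:** write *45 randomized, 30 expected to complete*.
- **Section 10.5:** change 22 to 23 for 17 completers at 25% attrition. Add one sentence saying that 45 randomized allows for up to 33% loss, a deliberate margin beyond the 25% seen in earlier work. If that was not the reasoning behind 45, the sponsor should state what was.
- **Any power figures quoted alongside:** label them as conditional on d being the standardized paired difference.

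The cost is a few text corrections. Enrolment stays at the 45 already planned, and neither the design nor the analysis changes. The drug service should be asked to confirm that its list runs to 45.

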### Visits 1-3

Days 7, 14, and 22 Following 1st positive Ovulation test:  
Administer Condition 1 Intervention (Placebo or Experimental).

Complete Interview Assessment of suicidality (SITBI).

Complete Computerized Tasks Measuring Inhibitory Control, Hopelessness, Rejection Sensitivity, and Threat Sensitivity. Assess side effects.

### Visits 4-6

[figure not shown]
Days 7, 14, and 22 Following 2nd positive Ovulation test:  
Administer Condition 2 Intervention (Placebo or Experimental).

Complete Interview Assessment of suicidality (SITBI).

Complete Computerized Tasks Measuring Inhibitory Control, Hopelessness, Rejection Sensitivity, and Threat Sensitivity. Assess side effects.

## 2 INTRODUCTION: BACKGROUND INFORMATION AND SCIENTIFIC RATIONALE

### 2.1 BACKGROUND INFORMATION

**Suicide is the second leading cause of death among women of reproductive age, yet we cannot reliably predict when a woman will attempt suicide.** Suicide accounts for 13% of all deaths among reproductive-age American females. Although existing models of suicide risk provide information about long-term, stable risk stemming from factors such as depression, interpersonal sensitivity, anxiety, or impulsivity, **little is known about when these or other factors will translate into acute risk for a suicide attempt**. By *directly studying suicidal individuals and focusing on biologic triggers and cognitive/behavioral mediators of acute changes in suicide risk*, the present research responds to public calls from the U.S. President, Congress, Surgeon General, and the NIMH-co-sponsored Suicide Research Prioritization Agenda, to identify strong predictors of acute suicide risk. Such work is imperative in developing targeted interventions for stabilizing and reducing suicidality, and will improve the precision and effectiveness of critical efforts to block suicide attempts.

**Perimenstrual (around menses) withdrawal from estradiol (E2) and progesterone (P4) may represent a time-varying biological mechanism of acute suicide risk.** The perimenstrual period, which is characterized by withdrawal from E2 and P4, is associated with more **hospitalization for suicide attempts**, **more lethal attempts**, and **suicide deaths**. *Despite these associations, no research has examined a causal role of perimenstrual ovarian steroid withdrawal in suicidality. The rationale for studying hormone withdrawal as a predictor of suicidality comes from work showing that withdrawal from normal levels of E2/P4, rather than differing absolute levels, precipitates affective symptoms and impulsivity in susceptible individuals*.

**The experiment** will test a model in which **perimenstrual E2/P4 withdrawal (vs. experimental luteal stabilization via transdermal E2 and oral micronized P4; STUDY AGENT) increases acute risk for suicidality** by negatively modulating mediating cognitive behavioral constructs (hopelessness, social appraisals, inhibitory control, threat sensitivity) and parallel clinical symptoms (depression, impulsivity, rejection sensitivity, anxiety). To maximize both safety and generalizability, we will study women with suicidal ideation but minimal imminent risk for suicide attempt.

**Theoretical Underpinning for Mediating Constructs.** Selection of mediating constructs through which ovarian steroid withdrawal is most likely to influence suicide risk is informed by **the Interpersonal Theory of Suicide**, which posits that suicidal behavior arises from two acute risk factors: **Suicidal Desire**—a wish to die, and **Suicidal Action Capacity**—a readiness to act on urges. *Suicidal desire* is strongly predicted by hopelessness and negative social appraisals (thwarted belongingness, perceived burdensomeness). *Suicidal action capacity* is predicted by poor inhibitory control and threat sensitivity—a tendency toward detection and reactions to threats (fostered by extreme stress exposure). *Because this is an integrative theory, the constructs measured here will allow testing of a variety of theories* (e.g., Neurocognitive Theory).

#### **Ovarian Steroid Changes Robustly Modulate Key Mediators of Suicidal Desire and Action Capacity**

1. **Hopelessness** repeatedly emerges as **the most robust** prospective predictor of suicidal desire in inpatients and outpatients. Furthermore, hopelessness and suicide share functional alterations of the dorsomedial prefrontal cortex, supporting a central role of hopelessness in suicidality.

**Ovarian steroid withdrawal may increase hopelessness (and associated symptoms of depression)**. In animals, ovarian steroid withdrawal increases depressive behavior via GABAergic and serotonergic mechanisms, whereas E2 specifically is known to exert antidepressant effects.

2. **Negative social appraisals predict suicidal desire**. Relationships are central to our ability to survive and thrive. Perceptions of social rejection are experienced as painful and increase suicidal desire—particularly in reproductive-age women. Additionally, suicidality is associated with altered function of brain regions associated with experiences of social exclusion and rejection.

**Ovarian steroid withdrawal may increase negative social appraisals (and associated symptoms of rejection sensitivity)**. In animals, E2 and P4 facilitate social motivation and behavior, and ovarian steroid withdrawal precipitates social withdrawal. In women, elevated luteal P4 correlates with social motivation and attention

to social-affiliative opportunities. The PI's longitudinal work indicates that ovarian steroid withdrawal predicts increased daily appraisals of social rejection in women at elevated suicide risk.

3. **Poor inhibitory control** enables suicidal desire to escalate into suicidal action. Suicidal ideation alone is a poor predictor of suicidal behavior; however, the addition of poor inhibitory control robustly predicts suicide attempts, suggesting its relevance for suicidal action capacity. Suicide attempters and victims show deficiencies in the functioning of inhibitory circuits.

**Ovarian steroid withdrawal may reduce inhibitory control (and increase associated symptoms of impulsivity)**. Cyclical E2/P4 withdrawal predicts poorer inhibitory control, greater impulsivity, and decreased frontal cortex inhibitory activity, while high, stable ovarian steroids increase frontal cortex inhibitory activation. Cyclical reductions in inhibition are particularly marked in women with low prefrontal dopamine, which corresponds to the greater impulsivity found in suicide victims. In animals, baseline impulsive behavior is a risk factor for greater sensitivity to ovarian steroid withdrawal.

4. **Threat sensitivity**, (defined as increased attention and reflexive responses to threats), **predicts suicidal behavior**. Repeated engagement of physiological stress systems also leads to HPA axis dysregulation, which prospectively predicts suicide attempts among chronically suicidal individuals. Other research in suicide victims indicate that generalized threat sensitivity and reactivity to stimuli in daily life are acutely elevated prior to fatal suicidal behavior.

**Ovarian steroid withdrawal may increase threat sensitivity (and associated symptoms of anxiety)**. In animals, E2/P4 withdrawal increases threat sensitivity and reactivity and causes threat-sensitizing alterations in associated brain circuitry, including the amygdala, the bed nucleus of the stria terminalis, and the periaqueductal grey, mediated by increased expression of GABAA receptor subunits that elicit anxiogenic effects of P4-derived neurosteroids. In women, correlates of suicidality including social stress, social isolation, lifetime abuse, impulsivity, and PTSD, predict greater effects of ovarian steroid withdrawal on threat sensitivity. Cyclical reductions in E2/P4 correlate with morphological and functional changes in CNS fear and anxiety circuitry, especially amygdala sensitivity.

Despite robust animal and correlational human evidence that E2/P4 withdrawal negatively modulates key mediators of suicide risk as outlined above, **the present research will be the first to experimentally confirm (or refute) a pathophysiologic role for steroid hormone withdrawal on suicide risk factors in humans, generally, and in at risk women, specifically**. The study delineates the within-person effects of ovarian steroid withdrawal on suicidal desire (via mediators hopelessness and social appraisals), and suicidal action capacity (via mediators inhibitory control and threat sensitivity).

